## 5.2 Data acquisition

To guarantee accurate and consistent data acquisition, a data acquisition system will be used as proposed in emergency medicine literature. (5,6) Data abstraction forms will be used, abstracters will be trained and interrater reliability will be measured using Cohen's kappa. Data abstraction will be blinded, which means that during data abstraction they will not be aware of the aim of the study.

### 5.2.1 Identification of subjects

We will collect data by searching the database via one or multiple ways, depending on the local registration infrastructure of the hospital. Options are searching for procedural code for endotracheal intubation, screening ICU admissions, screening resuscitation room logbooks, screening medication logbooks for intubation medication, searching ICD-10 code for cardiac arrest and other pathologies that could lead to intubation.

### 5.2.2 Abstraction forms

The abstraction form is attached as an appendix. All data will be abstracted via an electronic abstraction form. The data is completely anonymized and cannot be linked to individual patients. The abstraction forms will be pilot tested in the participating hospitals.

### 5.2.3 Quality of data acquisition

All abstractors are medical students, emergency medicine trainees or emergency medicine physicians. They will receive an abstractor manual and a standardized training program. During this training, abstractors will be instructed about definitions used in the abstraction form and how to interpret the medical charts. During the abstraction phase, abstractor meetings will be scheduled

to discuss coding rules and to resolve disputes. To assess interrater reliability, interrater variability will be measured using Cohen's Kappa. 10% of the charts will be reviewed by two abstractors, after which interrater agreement will be calculated. Interrater agreement will be assessed for the incidence of complications, method of intubations and sedation agent.

#### **5.2.4 Missing data**

All missing data will be reported in the results section.

### **6. STATISTICAL ANALYSIS**

Continuous data are presented as mean and standard deviation or median with interquartile range (IQR), depending on normality of data (graphically and numerically assessed), whereas nominal data are presented as absolute numbers and percentages. The Chi-square test or Fisher exact test will be used for comparison of nominal variables and the independent t-test and Mann Whitney test will be used when appropriate for comparison of continuous variables across treatment groups.. For all tests a  $p < .05$  will be used to indicate statistical significance. All tests are two-tailed. Statistical analysis will be performed using IBM SPSS Statistics Premium' V 22 for Windows (IBM Corp. Released 2011. IBM SPSS Statistics for Windows, version 22.0. Armonk, NY: IBM Corp.).

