## **SUMMARY**

### **Rationale:**

**Objective:** To describe and evaluate the practice and safety of endotracheal intubation of patients in Dutch emergency departments (ED).

**Study design:** Retrospective cohort study.

**Study population:** Patients who underwent endotracheal intubation in the ED of one of the participating hospitals in the Netherlands

**Intervention (if applicable):** Not applicable.

**Main study parameters:** The practice of, indications for and incidence of complications of endotracheal intubation in the ED.

**Nature and extent of the burden and risks associated with participation, benefit and group relatedness:** Due to the retrospective design, there is no active involvement of patients or randomisation, and only data relevant to the study will be collected. Data collection will be completely anonymized.

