## **1. INTRODUCTION AND RATIONALE**

Endotracheal intubation can be a lifesaving intervention for critically ill patients in the emergency department (ED). Endotracheal intubation is, however, a high-risk procedure with many potential complications, which seem to be even more prevalent when carried out in the ED compared to for example the operating theater(5). This is possibly due to multiple reasons such as a sicker population, non-elective setting, a higher variability among indications for intubation or competence of providers.

Internationally, large registries were established and multiple observational studies have been performed to gain more information about the methods, safety and complications of intubations in the ED. For example, a multicenter study in Australia and New Zealand set up the ANZEDAR (The Australian and New Zealand Emergency Department Airway Registry) and reported on the practice, indications, success rate and safety of 3710 intubations performed in emergency departments (1). The same was done with the NEAR (National Emergency Airway Registry) including ED's from the United States, Canada and Australia; in a prospective, multicenter international registry of intubations in emergency departments a total number of 17,583

intubations were registered and analyzed (3). These studies gave more insight into patient demographics, staff characteristics, pharmacologic agents used and complication rates. In the UK, a national audit project (NAP4) showed that there were relatively far more complications of airway management in the ED compared to the operating theater and that complications in the ED were more likely to result in harm or death than complications in the operating theater. Individual case review identified avoidable deaths and areas of care that need improvement (5,6).

While in recent years these studies have added to our knowledge of ED airway management, there is still a lack of high-quality studies and there is a strong argument for increased research. To date, no studies have been published of airway management in Dutch EDs. We therefore have no knowledge about any factors possibly influencing intubation outcomes and complications nor comparability with international data. Among these are factors that have been associated with preventable harm and death and insight into these factors could be used for improvement of the safety of airway management in Dutch EDs (6).

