This study is therefore intended to provide a comprehensive review of the clinical practice and characteristics of endotracheal intubations within Dutch EDs. The results could potentially be used for comparative analysis against global datasets. Additionally, the insights gained from this study will shed light on existing gaps prevalent in the current registration processes of intubations in the Netherlands. Furthermore, these insights could act as a stepping stone for future investigations that can lead to a deeper understanding of the methodologies, safety protocols, and associated complications of endotracheal intubations within Dutch EDs.

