## 2. OBJECTIVES

### **Primary outcome:**

Describing characteristics of the practice of endotracheal intubation in Dutch EDs, including information about patient demographics, indications for endotracheal intubation, intubation performer characteristics, equipment and medication used and complications due to intubation.

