#### **4.4 Sample size calculation**

Not applicable. Data of all patients eligible for the study will be included.

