### **7. ETHICAL CONSIDERATIONS**

#### **7.1 Regulation statement**

The patients will not be asked for signed informed consent. The data collection will be retrospective and completely anonymized. Patients are not randomized. In addition, this research focuses on standardized care and no new or additional actions were carried out. We suspect to screen at least 500-1000 patients for inclusion and find it not feasible to ask every patient for consent retrospectively. This would cost a disproportionate amount of effort and possibly excludes a large number of patients due to not being able to reach the patient, especially since it is expected that a high proportion of the patients died due to the seriousness of the underlying disease. Also, to a lesser amount it may cause a selection bias because it could be more difficult to get consent in the case of complicated intubations. Data will be derived from electronic patient files, from 2019up to

now. Asking for informed consent from patients who had an intubation 3 years ago would not outweigh disadvantages for the patient.

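### Section 6 plans no confidence intervals for the complication incidences and practice percentages that are the study's main product, and fixes no denominator for the complications

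*Combined protocol and SAP*

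**What the plan says.** The Summary gives the main study parameters as "The practice of, indications for and incidence of complications of endotracheal intubation in the ED". Section 2 makes the primary outcome descriptive: "Describing characteristics of the practice of endotracheal intubation in Dutch EDs", with complications among the items to be described.

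Section 6 covers presentation and testing. For categorical variables, "nominal data are presented as absolute numbers and percentages". Continuous variables get a mean with SD or a median with IQR. The remaining tools are chi-square, Fisher, t and Mann-Whitney tests at the 5% level across treatment groups that are not defined; "All tests are two-tailed". No confidence interval, standard error of a proportion or precision target appears in the document.

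On size, Section 4.4 reads "Not applicable. Data of all patients eligible for the study will be included". The only figure is in Section 7.1, in the argument for waiving consent: "We suspect to screen at least 500-1000 patients for inclusion".

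Section 5.1 codes complications three ways: occurred, explicitly absent, or not mentioned. Section 5.2.1 lets the method of finding cases differ between hospitals.

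**The concern.** When the aim is estimation, the precision of each estimate is part of the result. Section 6 directs its inferential tools at p-values between groups, which do not bear on the primary outcome, and leaves the primary outcome as bare percentages. The SD and IQR do not fill the gap, because they describe spread between patients and not the uncertainty of an estimate.

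Including every eligible chart does not remove the uncertainty. The data come from the participating hospitals in 2019–2023, while the objective is worded for Dutch EDs. Section 5.1 lists many separate complications, and any with few or no events would be the hardest to read without a limit beside the count. Section 1 adds that "The results could potentially be used for comparative analysis against global datasets", and one registry it cites holds "3710 intubations performed in emergency departments". If that use is made of the results, a reader needs to know how large a difference chance alone could produce.

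There is a second gap. With three-way coding, a complication percentage has no single denominator until the plan says how charts with no statement are counted. An interval cannot be defined before that is settled.

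**Working it through.** The plan states no power, precision or expected rate, so there is no figure of its own to reproduce. The check asks how much uncertainty the bare percentages would hide.

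**Inputs from the documents.** 500 and 1000 (Section 7.1, patients screened, given as a minimum); registry sizes 3710 and 17,583 (Section 1).

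**Assumptions.** 500 or 1000 patients are actually included. The event rates are illustrative. Charts are independent in steps 1 to 3.

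**1. Zero events, exact (Clopper-Pearson) upper limit,** 1 − 0.025^(1/n):
- n = 500: 1 − 0.025^(1/500) = 0.74%
- n = 1000: 1 − 0.025^(1/1000) = 0.37%

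**2. Wilson 95% interval,** [p + z²/2n ± z√(p(1−p)/n + z²/4n²)] / (1 + z²/n), z = 1.96:

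| Observed | n = 500 | n = 1000 |
|---|---|---|
| 2% (10 or 20 events) | 1.1–3.6% | 1.3–3.1% |
| 5% (25 or 50) | 3.4–7.3% | 3.8–6.5% |
| 20% (100 or 200) | 16.7–23.7% | 17.6–22.6% |

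At n = 500, an observed 2% is compatible with true rates that differ about threefold (3.6/1.1 = 3.3).

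**3. Difference from a registry, should anyone make that comparison.** The 95% half-width is 1.96√(p(1−p)(1/n + 1/m)), taking the same rate p in both sources:
- p = 5%: from 1.39 points (n = 1000, m = 17,583) to 2.04 points (n = 500, m = 3710)
- p = 20%: from 2.55 to 3.73 points for the same pairs

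**4. Clustering.** The design effect is 1 + (k − 1) × ICC, where k is patients per hospital and ICC is the intra-hospital correlation. The documents give neither k, the number of hospitals nor the ICC. Purely as assumptions, take 5 to 10 hospitals and an ICC of 0.01 to 0.05:
- smallest: 500/10 = 50 per hospital, 1 + 49 × 0.01 = 1.49; widening √1.49 = 1.22
- largest: 1000/5 = 200 per hospital, 1 + 199 × 0.05 = 10.95; widening √10.95 = 3.31

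The range is too wide to support any single multiplier. The top end is also implausible for rare events. At a 2% rate, an ICC of 0.05 implies a between-hospital SD of √(0.05 × 0.02 × 0.98) = 3.1 percentage points, which exceeds the rate itself.

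**5. Denominator.** With x complicated intubations, N charts and U charts with no statement, the incidence is x/N if silence counts as uncomplicated and x/(N − U) if silent charts are left out. The second exceeds the first by a factor N/(N − U). The plan does not say which is meant, or whether both will be shown.

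**The case against.** The strongest reply is that nothing essential is lost. Section 6 promises counts as well as percentages, so anyone with the numerator and denominator can compute a Wilson or exact interval. That is right. A reader might infer that rare or zero complications cannot be interpreted at all, and the documents do not support that. What stands is narrower: the presentation and the denominator are not pre-specified, and an interval that reflects variation between hospitals cannot be recovered from pooled counts.

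Second, comparison with the international registries is only a possible later use. Section 6 plans no such analysis, so a reader should not infer that a planned comparison is invalid. The case for intervals rests on the primary outcome itself.

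Third, clustering matters only for some targets. If inference is confined to the participating hospitals, they are fixed strata and the design effect in step 4 does not apply. It applies if they stand for Dutch EDs in general. The objective is worded that way, although no sampling of hospitals is described. A reader might take it that the pooled intervals must be several times wider, but the documents give no basis for a figure.

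Fourth, one could ask Section 4.4 for a precision target. In a retrospective cohort that takes every eligible patient, such a statement would change no decision, and 500–1000 is a screening figure. Section 4.4 can stand.

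Finally, under-recording in charts may be a larger source of error than sampling. Intervals do not address it, but that is no reason to omit them.

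**Conclusion.** The point holds as a gap in reporting and pre-specification. The study's main estimates are to appear without any measure of sampling uncertainty, and the complication percentages lack a defined denominator. This does not invalidate the design, and it is cheap to put right.

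On the assumption that 500 to 1000 patients are included and charts are independent, zero events would leave room for a true rate of up to 0.74% to 0.37%, and an observed 2% would carry an interval of 1.1–3.6% to 1.3–3.1%. The included number may be lower or higher than the screening figure. Any further widening from clustering depends on an ICC and hospital sizes that the documents do not give.

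**What to change.** Add to Section 6:

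> Each complication incidence and main practice percentage is reported with its denominator (for complications, stating how charts with no statement about complications are counted) and a two-sided 95% confidence interval (Wilson; exact Clopper-Pearson for zero events). For pooled percentages, hospital-specific percentages with their own intervals are shown alongside. Where a pooled figure is generalised to Dutch EDs, its interval uses a cluster-robust (marginal) method if the number of hospitals allows.

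A marginal method is preferable here because a random-intercept logistic model estimates a hospital-conditional probability, so its interval is not directly one for the pooled percentage. Neither approach is useful with zero events. There the exact limit should be reported as one that treats charts as independent.

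The cost is a few sentences and some extra columns in the tables, with no new data beyond keeping a hospital identifier in the analysis file. The downside is that the reported figures will look less precise. The intervals will cover sampling error only, and the report should say so.

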### **3. STUDY DESIGN**

This is a retrospective cohort study using electronic patient charts of patients who underwent endotracheal intubation in the emergency departments of the participating hospitals.

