### **5. METHODS**

#### **5.1 Study parameters**

- Intubator characteristics:
  - Specialty
    - Emergency medicine
    - Anesthesia
    - Intensive care medicine
    - Other
  - Seniority
    - Consultant
    - Resident

- Junior doctor

- Indication for intubation:
  - Trauma
  - Burns
  - Drowning
  - Overdose/ingestion
  - Respiratory failure
  - Cardiac arrest (active cardiac arrest)
  - Post-cardiac arrest
  - Stroke
  - Seizure
  - Altered mental status due to other cause (if altered mental status due to stroke, intoxication, seizure or post-cardiac arrest then score as the primary cause)
  - Sepsis
  - Cardiac failure
  - Airway obstruction
  - GI bleed
  - Anaphylaxis
  - Other
- Sedation agent used (Ketamine, etomidate, propofol, midazolam)
- Paralytic agent used (Rocuronium / Succinylcholine)
- Method of intubation
  - Direct laryngoscopy
  - Video (hyperangulated or direct)
  - Fiberoptic
  - Surgical airway
  - Use of airway adjuncts? If yes, which ...
- Patient characteristics: age (years), gender (male/female), weight/obesity (BMI).

- Vital parameters before intubation (respiratory rate, saturation, systolic blood pressure (SBP), heart rate).
- Was a pre-intubation airway assessment performed? Yes / no / missing
- If yes, were there any signs of a difficult intubation?
- Performance and mode of pre-oxygenation; no pre-oxygenation / nasal canula / NRM / mask ventilation / NIV / missing
- Was capnography used during intubation? Yes / no / missing
- The occurrence of complications of endotracheal intubation. Complications will be identified in two ways. The first option is that a complication is explicitly stated in the electronic medical record. The second option is that there are significant changes in vital signs as described in more detail below. The following complications will be registered:
  - significant decrease of peripheral oxygen saturation (SpO2). Defined as a desaturation of >10% from baseline or as defined by the treating physician
  - significant decrease of blood pressure. Defined as a systolic pressure <90mmHg with a drop of >20% from baseline or as defined by the treating physician.
  - significant increase of blood pressure. Defined as a systolic pressure > 160mmHg with a rise of >20% from baseline, or as defined by the treating physician.
  - significant bradycardia. Defined as a heart rate < 40/min and a drop of > 20% from baseline, or as defined by the treating physician.

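### Section 6 plans only unadjusted significance tests, with reference to undefined treatment groups, in a non-randomised chart review; if complications are compared by treatment, the p-values can be confounded by severity and indication

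*Combined protocol and SAP*

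**What the plan says.** Section 6 gives the whole analysis plan in one paragraph. After the descriptive summaries it states that "The Chi-square test or Fisher exact test will be used for comparison of nominal variables", and that a t-test or Mann-Whitney test serves for "comparison of continuous variables across treatment groups". A p-value below .05 "will be used to indicate statistical significance", and "All tests are two-tailed". No regression, stratification, matching or weighting appears there or elsewhere, and the treatment groups are not defined.

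On design, section 3 says "This is a retrospective cohort study using electronic patient charts", and section 7.1 says "Patients are not randomized". The only objective, in section 2, is descriptive; the Summary adds evaluation of practice and safety and lists the incidence of complications among the main parameters. The Introduction motivates the work by the fact that there is "no knowledge about any factors possibly influencing intubation outcomes and complications", and says that such insight could improve safety.

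Section 5.1 records sedative, paralytic agent, method of intubation, and the operator's specialty and seniority. It also records indication, age, gender, BMI, "Vital parameters before intubation (respiratory rate, saturation, systolic blood pressure (SBP), heart rate"), and signs of a difficult airway where an assessment was made.

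**The concern.** Treatment groups in routine care are formed by clinical choice. If that choice depends on how ill the patient is, or on why intubation is needed, and those same features raise the risk of a complication, a crude test compares different kinds of patient. A treatment given mainly to the sickest patients can then look harmful when it has no effect, and a protective one can look neutral. Stratifying by hospital would not remove this, because the choice is made patient by patient within each hospital.

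The protocol recognises case mix itself: the Introduction offers a sicker population, more varied indications and differing provider competence as possible reasons why complications are more frequent in the ED. Section 6 has no step that accounts for any of these. In a study motivated by safety improvement, a significant crude difference between drugs or devices is likely to be read as a finding about the drug or device.

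**Working it through.** **No figure to reproduce.** Section 4.4 gives no sample size calculation, and no effect size or power is stated. The calculation below is illustrative.

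**Inputs from the documents.** Two-sided test at 0.05 (section 6). Total N of 500 and 1000, borrowed from section 7.1, which expects at least that range to be screened; it is not an analysed sample size.

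**Assumptions, not in the documents.** Two treatment groups, A and B; one binary severity factor present in 30% of patients; complication risk 10% in non-severe patients; no true treatment effect.

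**Formulas.** Let s = 0.30 be the share severe, r1 and r0 the risks in severe and non-severe patients, and a1 and a0 the proportions of each given A.

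- Crude risk in A = [s·a1·r1 + (1−s)·a0·r0] / [s·a1 + (1−s)·a0]
- Crude risk in B = the same with 1−a1 and 1−a0 in place of a1 and a0

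**Worked case** (r1 = 30%, r0 = 10%, a1 = 70%, a0 = 30%):

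- A: (0.21×0.30 + 0.21×0.10) / 0.42 = 0.084/0.42 = 20.0%
- B: (0.09×0.30 + 0.49×0.10) / 0.58 = 0.076/0.58 = 13.1%
- Crude risk ratio 0.200/0.131 = 1.53, where the truth is 1.00

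**Range.** The last column is the rate of p<.05 for the crude chi-square test with no true effect, from 20,000 simulated studies per setting.

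| r1 | a1 / a0 | Risk A | Risk B | Crude RR | p<.05 at N = 500 / 1000 |
|---|---|---|---|---|---|
| 30% | 40% / 40% (no link) | 16.0% | 16.0% | 1.00 | 5% / 5% |
| 20% | 60% / 40% | 13.9% | 12.2% | 1.14 | 9% / 12% |
| 30% | 70% / 40% | 18.6% | 13.5% | 1.37 | 34% / 58% |
| 30% | 70% / 30% | 20.0% | 13.1% | 1.53 | 55% / 83% |
| 40% | 80% / 40% | 23.9% | 13.8% | 1.73 | 83% / 98% |
| 30% | 80% / 20% | 22.6% | 11.9% | 1.90 | 88% / 99% |

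The risk ratio does not depend on N; only the false-positive rate does, and it rises with N. In the 70%/30% case, a treatment that truly lowers risk by a factor of 0.70 gives 0.140/0.131 = 1.07.

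**With adjustment.** A Mantel-Haenszel test stratified on the severity factor brings the rejection rate back to about 5% in every row. That holds because the simulated factor is the only confounder and is never missing; real charts will not guarantee either.

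**A link the documents do contain.** Section 5.1 defines hypotension from vital signs as a systolic pressure below 90 mmHg together with a fall of more than 20%. The fall needed is therefore the larger of 20% and (baseline − 90)/baseline: 20% at a baseline of 112.5 or lower, 25% at 120, 40% at 150 and 50% at 180. On this route the outcome depends on baseline pressure by definition, so groups that differ in baseline pressure are not judged by the same relative fall.

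**The case against.** Four points on the other side have force.

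- **The comparison is not stated.** Section 6 does not name complications as the outcome compared, nor drug, device or operator as the grouping. Grammatically, the reference to treatment groups attaches to continuous variables. A reader might infer that the plan commits to comparing complications by drug, device and operator; the documents do not say so. Sedative, paralytic and method are the treatments recorded and complications are a main nominal parameter, so the reading is natural, but it remains a reading. Operator is its least direct extension.
- **The objective is descriptive.** A crude difference misleads only if it is read as an effect, and the sentence about unknown factors is background rather than an objective. This stands, but pure description needs no significance tests between treatment groups, and section 6 plans them.
- **Confounding is not shown.** A reader might infer that treatment is known to follow severity. The documents do not say how treatment is chosen, so confounding is plausible and expected but not demonstrated.
- **Adjustment is not a cure.** A reader might infer that everything needed to adjust is already collected. Section 5.1 lists no consciousness score, comorbidity or vasopressor use; the abstraction form is not in the text and might add some. Airway signs exist only where an assessment was made. An adjusted p-value could carry authority that it has not earned.

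These points narrow the claim and shape the remedy. They do not supply the missing definition of groups or any protection against case-mix differences.

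**Conclusion.** The point holds as a conditional one. The documents establish unadjusted tests, undefined groups, no randomisation and no planned adjustment. They do not establish which comparisons will be made, how treatment is chosen, or how large the bias would be. If complications are compared by treatment, the crude p-values can be confounded by severity and indication. The illustrative range for a treatment with no effect is a risk ratio of about 1.14 to 1.9, with false-positive rates from 9% (mild, N = 500) to about 99% (strong, N = 1000). Severity prevalence, risks and treatment choice are all assumed, N is a screening expectation, and a single two-group contrast is assumed although four sedatives are listed. With no link between severity and treatment there is no bias. The change should be made before analysis; the descriptive primary objective stands without it.

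**What to change.** First define in section 6 which groups and which outcomes are compared. Then choose one of two routes.

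(a) Describe complications by group with 95% confidence intervals and no significance tests. This is the simpler route and fits the objective in section 2.

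(b) Report an adjusted association with a 95% confidence interval, from logistic or robust Poisson regression, using variables already in section 5.1: age, BMI, indication group, pre-intubation systolic pressure, saturation and heart rate, signs of a difficult airway, and operator, plus hospital. Where events are too few to support the model, fall back on (a).

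Route (b) also needs three rules:

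- how charts silent on complications, one of the three outcome codes in section 5.1, enter the analysis;
- how missing baseline values are handled. Section 5.2.4 only reports missingness, and a missing baseline also prevents classification of outcomes defined by change from baseline, so imputing covariates alone does not settle it;
- how patients intubated during active cardiac arrest are handled, since pre-intubation pressure and saturation are not ordinary covariates for them.

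Under either route, label results as associations with residual confounding possible, and do not present crude p-values as factors that influence complications.

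Cost: route (a) is a wording change. Route (b) is a modest extra analysis, with charts lacking baseline values either lost or imputed.
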